7.3 PHARMACODYNAMIC EVALUATIONS

7.3.1 *Blood Sample Collection and Handling*

Blood samples for PD assessments will be drawn at the time points indicated in the [Time and Events Schedule](#). The exact date and time of blood sampling must be recorded in the source documents and on the eCRF.

Blood samples for the assessment of LH, FSH, E2, SHBG, insulin, and leptin, C-peptide, and HBA1c (HBA1c at Visits 2 and 5 only) in plasma will be collected and handled as specified in the central laboratory manual.

Additional back-up samples will be collected at every visit and stored for future, exploratory use.

After appropriate labeling, the plasma samples will be stored below -70°C at the clinical site. Thereafter, the frozen plasma samples will be transported/shipped on dry ice to the central laboratory (BARC, Gent, Belgium), where they will be collected and kept frozen below -70°C until analysis.

Further procedures for sample collection, shipment, processing, and storage are described in the laboratory manual.

7.3.2 *Bioanalysis*

Plasma samples for PD assessments will be analyzed by BARC (Gent, Belgium), using a validated analytical method.

After completion of the analytical study, the study samples will be kept deep frozen until three months after issuing of the final Clinical Study Report, or six months after issuing of the draft Clinical Study Report, whichever comes first. Then, upon agreement with the Sponsor Representative, the study samples will either be transferred to the sponsor facilities, or kept deep frozen at BARC (Gent, Belgium) for a longer period of time (as to be agreed with the Sponsor) at $-70^{\circ}\text{C} \pm 6^{\circ}\text{C}$, or destroyed at BARC (Gent, Belgium).

Samples that remain after protocol-specific assessments have been performed may be used for further exploratory work on PK, metabolites, plasma protein binding, protein analysis, and biochemistry. No human DNA or RNA analysis will be performed.

7.3.3 *Pharmacodynamic Endpoints*

Changes in plasma concentrations of LH, FSH, E2, SHBG, leptin, insulin, C-peptide, and HBA1c from baseline over time will be evaluated.

7.4 EFFICACY EVALUATIONS

7.4.1 *Efficacy Variables*

Efficacy evaluation in this study will be based on hot flash severity and frequency as well as HFRDIS, assessed via ePRO diary, and the following paper-based questionnaires: LSEQ, SDS, and GCS, as described in the following sections. All questionnaires used in the study will be validated and available in the local language of the clinical sites.

7.4.1.1 *HOT FLASH FREQUENCY AND SEVERITY*

Hot flashes severity and frequency will be assessed on an ad hoc basis, but at a minimum twice-daily (morning and evening), via ePRO diary from screening (Visit 1) through the follow-up visit (Visit 6). Data on hot flash severity and frequency collected during the screening period will serve as baseline for Hot Flash Score and Hot Flash Frequency.

Night sweats should be recorded no later than morning upon awakening to start a new day.

The severity of hot flashes is defined clinically as follows (according to the FDA and EMA Guidance for Industry [19,20] and the National Institutes of Health (NIH) Hot Flash Workshop [21]):

- **Mild:**
Sensation of heat without sweating/dampness. If at night, patient doesn't wake up but later notices damp sheets or clothing.
- **Moderate:**
Sensation of heat with sweating/dampness, but able to continue activity. If at night, patient wakes up because she is feeling hot and/or is sweating, but no action is necessary other than rearranging the bed sheets.
- **Severe:**
Sensation of intense heat with sweating, causing disruption of activity. If at night, patient wakes up hot and is sweating and needs to take action (e.g., removing layers of clothes, open the window, or get out of bed).

The Hot Flash Score (based on severity and frequency) is calculated as follows [22]:

$$(\text{number of mild hot flashes/day} \times 1) + (\text{number of moderate hot flashes/day} \times 2) + (\text{number of severe hot flashes/day} \times 3)$$

Higher scores indicate worse symptoms. There is no maximum score since the score is patient-dependent for both number and severity.

7.4.1.2 *HOT FLASH RELATED DAILY INTERFERENCE SCALE (HFRDIS)*

Perceived hot flash interference on daily activities will be evaluated every 4 weeks from the start of study drug intake (Visit 2) through the follow-up visit (Visit 6) using the HFRDIS. The HFRDIS will be completed at the clinical site in the ePRO diary, at any time during the visit.

The HFRDIS is a 10-item scale which measures a woman's perceptions of the degree to which hot flashes interfere with 9 daily life activities (work, social activities, leisure, sleep, mood, concentration, relations with others, sexuality, enjoying life); the 10th item measures interference with overall quality of life [23]. This scale was modeled after items on the Brief Pain Inventory [24] and Brief Fatigue Inventory [25] both of which assess the extent to which pain or fatigue interfere with daily life. Subjects will be asked to rate the extent to which hot flashes have interfered with each item during the previous 4-week time interval using a 0 (do not interfere) to 10 (completely interfere) scale. Recent structural equation modeling suggests this is a unidimensional scale best represented by an overall mean score (sum of items/10) [26].

Scoring of each item of the HFRDIS is illustrated in [Attachment 1](#).

7.4.1.3 *LEEDS SLEEP EVALUATION QUESTIONNAIRE (LSEQ)*

Subjects' sleep quality will be evaluated every 4 weeks from the start of study drug intake (Visit 2) through the follow-up visit (Visit 6) using the LSEQ. The questionnaire will be paper-based, administered at the clinical site at any time during the visit.

The LSEQ is a 10-item self-rated questionnaire which assesses subjects' aspects of sleep and early morning behavior. The questions are grouped into 4 chronological areas: the ease of getting to sleep, the perceived quality of sleep, the ease of awaking from sleep, and the integrity of early morning behavior following wakefulness [27]. The LSEQ is a visual analogue scale which requires respondents to place marks on a group of 10-cm lines representing the changes they have experienced in a variety of symptoms since the beginning of treatment. Lines extend between extremes like "more difficult than usual" and "easier than usual". Responses are measured using a 100-mm scale and are averaged to provide a score for each domain.

A copy of the LSEQ is provided in [Attachment 2](#).

7.4.1.4 *GREENE CLIMACTERIC SCALE (GCS)*

Changes in climacteric symptoms will be evaluated every 4 weeks from the start of study drug intake (Visit 2) through the follow-up visit (Visit 6) using the GCS. The questionnaire will be paper-based, administered at the clinical site at any time during the visit.

The GCS is a 21-item scale which provides a brief but comprehensive and valid measure of climacteric symptomatology [28]. Each item is rated by the subject according to its severity using a four-point rating scale from 0 (none) to 3 (severe). The first 20 items of the scale combine into three main independent symptom measures: psychological symptoms (items 1 to 11; score 0 to 33), physical symptoms (items 12 to 18; score 0 to 21), and vasomotor symptoms (items 19 to 20; score 0 to 6), by summing up the individual item scores. Item 21 is a probe for sexual dysfunction. The total score can range from 0 to 63. Higher scores indicate worse symptoms.

Scoring of each item of the GCS is illustrated in [Attachment 3](#).

7.4.1.5 *SHEEHAN DISABILITY SCALE (SDS)*

Subjects' functional impairment of life will be evaluated every 4 weeks from the start of study drug intake (Visit 2) through the follow-up visit (Visit 6) using the SDS. The questionnaire will be paper-based, administered at the clinical site at any time during the visit.

The SDS is a composite of 3 self-rated items designed to measure the extent to which 3 major sectors in a patient's life are impaired by panic, anxiety, phobic, or depressive symptoms [29]. The patient rates the extent to which his/her 1- work/school, 2- social life, and 3- family life are impaired by his/her symptoms on a 10-point visual analog scale. The 3 items may be summed into a single dimensional measure of global functional impairment that ranges from 0 (unimpaired) to 30 (highly impaired). It is recommended that clinicians pay attention to patients who score 5 or greater on any of the 3 scales, because such high scores are associated with significant functional impairment [30].

A copy of the SDS is provided in [Attachment 4](#).

7.4.1.6 *BODY COMPOSITION*

Lean body mass, fat mass, muscle mass, bone mass/density will be assessed by DEXA at Visits 2 and 5.

7.4.2 *Efficacy Endpoints*

7.4.2.1 *PRIMARY ENDPOINT*

- Change from baseline to Week 12 in weekly Hot Flash Score

7.4.2.2 *SECONDARY ENDPOINTS*

- Changes from baseline over time in weekly Hot Flash Score and Hot Flash Frequency;
- Change from baseline over time in HFRDIS score;
- Changes from baseline over time in LSEQ, GCS, and SDS score.

7.4.2.3 *EXPLORATORY ENDPOINT*

The change from baseline to Week 12 in body composition (lean mass, fat mass, bone mass/density) will be explored.

7.5 SAFETY EVALUATIONS

Safety evaluation in this study will be based on AEs, clinical laboratory tests, plasma bone density marker concentrations, ECG, vital signs, and physical examination, as described in the following sections.

7.5.1 *Safety Variables*

7.5.1.1 *ADVERSE EVENTS*

Adverse events will be monitored continuously from informed consent until the last study-related activity. At regular intervals during the study, subjects will be asked non-leading questions to determine the occurrence of any AEs. All AEs reported spontaneously during the course of the study will be recorded as well.

For detailed definitions and reporting procedures of AEs, see [Section 10](#).

7.5.1.2 *CLINICAL LABORATORY TESTS*

Blood and urine samples will be collected at the time points indicated in the [Time and Events Schedule](#).

Blood samples will be collected and handled as specified in the central laboratory manual. Biochemistry and hematology testing will be performed on these samples, as well as coagulation and serology (HbsAg, anti-HCV and HIV antibodies) on the sample from screening. All blood samples for clinical laboratory tests should be taken in a fasted state (overnight fast for at least 10 hours; intake of water will be allowed until one hour before study drug intake) for unbiased glucose, insulin, and C-peptide determination.

Standard laboratory tests will be performed by the central laboratory BARC (Gent, Belgium). Further procedures for sample collection, shipment, processing, and storage are described in the laboratory manual provided by the central laboratory.

The following clinical laboratory tests will be performed on the samples:

- Biochemistry: sodium, potassium, uric acid, creatinine, calcium, AST, ALT, urea, alkaline phosphatase (ALP), gamma glutamylaminotransferase (GGT), albumin, glucose (fasted for at least 10 hours) total bilirubin (and direct bilirubin in case $>1.3 \times \text{ULN}$), creatine kinase (CK), and total protein;
- Coagulation: international normalized ratio (INR), activated partial thromboplastin time (aPTT) (at screening only);
- Hematology: white blood cell (WBC) count with differential (neutrophils, lymphocytes, eosinophils, monocytes, basophils), hemoglobin, hematocrit, red blood cell (RBC) count, platelet count.

Urinalysis will be performed on site using a commercial urine dipstick (dipstick will be provided by BARC to the clinical sites). In case the dipstick result is positive, a urine sample has to be shipped to BARC for urine sediment analysis.

A urine pregnancy test will be performed at screening, as well as a urine drug screen for amphetamines, tricyclic antidepressants, cannabinoids, cocaine, tetrahydrocannabinol, or opiates.

The Investigator must review the laboratory report, document this review, and record any change occurring during the study he/she considers to be clinically relevant in the source documents and in the AE section of the eCRF. Laboratory values outside the laboratory normal range will be flagged and their clinical relevance will be assessed by the Investigator. A copy of all laboratory reports must be filed in the subject's medical records.

Samples that remain after protocol-specific assessments have been performed may be used for further exploratory work on PK, metabolites, plasma protein binding, protein analysis, and biochemistry. No human DNA or RNA analysis will be performed.

7.5.1.3 BONE DENSITY MARKERS

Plasma concentrations of the bone density markers BALP and CTX will be assessed at Visits 2 and 6.

Blood samples for the assessment of BALP and CTX in plasma will be collected and handled as specified in the central laboratory manual.

After appropriate labeling, the plasma samples will be stored below -70°C at the clinical site. Thereafter, the frozen plasma samples will be transported/shipped on dry ice to the central laboratory (BARC, Gent, Belgium), where they will be collected and kept frozen below -70°C until analysis.

Further procedures for sample collection, shipment, processing, and storage are described in the laboratory manual.

7.5.1.4 *VITAL SIGNS*

Vital sign parameters will be assessed after 5 minutes in supine position at the time points indicated in the [Time and Events Schedule](#).

The vital sign parameters that will be assessed are body temperature (oral), supine systolic and diastolic blood pressure (SBP and DBP, respectively) and pulse rate. These parameters will be measured using a completely automated device consisting of an inflatable cuff and an oscillatory detection system. All values will be registered on a built-in recorder so that measurements are observer-independent.

Any change from baseline in vital sign values occurring during the study that is considered to be clinically relevant or that requires concomitant medication as judged by the Investigator should be recorded in the source documents and the AE section of the eCRF.

7.5.1.5 *ELECTROCARDIOGRAM*

Twelve-lead ECGs will be recorded after 5 minutes in supine position at the time points indicated in the [Time and Events Schedule](#).

The interpretations of the ECGs will be performed by the Investigator or his/her designee at the clinical site. Any change from baseline ECG occurring during the study that is considered to be clinically relevant by the Investigator should be recorded in the source documents and the AE section of the eCRF.

A local ECG reader will be used.

7.5.1.6 *PHYSICAL EXAMINATION*

Physical examination will be performed at the time points indicated in the [Time and Events Schedule](#).

Physical examination includes height, weight, and waist circumference (height at screening only). To obtain the actual body weight, subjects must be weighed lightly clothed. The height should be measured barefoot. Waist circumference will be measured according to NIH guideline (see [Attachment 5](#)).

Any change in physical examination occurring during the study that is considered to be clinically relevant by the Investigator should be recorded in the source documents and the AE section of the eCRF.

7.5.2 *Safety Endpoints*

Safety endpoints are:

- AE frequency and severity from first dose of study drug through the last visit;
- Changes from baseline over time in hematology and biochemistry concentrations;
- Changes from baseline over time in vital sign and ECG assessments;
- Changes from baseline over time in BALP and CTX levels.

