Sampling for pharmacokinetic assessments ^h			X	X	X	X	
Sampling for pharmacodynamic assessments ^{h,i}		X	X	X	X	X	X
Hot Flashes Severity and Frequency ^j		X	X	X	X	X	X
Hot Flash Related Daily Interference Scale ^k			X	X	X	X	X
Leeds Sleep Evaluation Questionnaire ^l			X	X	X	X	X
Greene Climacteric Scale ^l			X	X	X	X	X
Sheehan Disability Scale ^l			X	X	X	X	X
Clinical laboratory tests and urinalysis ^m		X	X	X	X	X	X
Bone density markers ⁿ			X			X	
Vital signs ^o		X	X	X	X	X	X
ECG ^p		X	X	X		X	X
Randomization			X				
ePRO training		X					
Dispensing of study drug ^q			X	X	X		
Intake of study drug ^r			X	X	X	X	
Compliance ^s				X	X	X	
Concomitant therapies ^t		X	X	X	X	X	X
Adverse events ^t		X	X	X	X	X	X

Footnotes on the next page.

- a. All visits need to be planned in the morning, fasted (for unbiased glucose, insulin, and C-peptide determination). Visit 2 should be planned to allow for first intake of study drugs at the clinical site, between 7:00 and 10:00 AM. For each subject, all visits during the treatment period subsequent to Visit 2 should be planned at the same time of the day, in the morning. A deviation of ± 1 day is allowed on the visits during the treatment period subsequent to the first study drug intake (Visits 3-5).
- b. Screening is to be performed within 4 weeks prior to the first intake of study drug, with a minimum of 7 days to allow for baseline data collection of Hot Flash Score and Hot Flash Frequency.
- c. Two to 3 weeks after the last intake of study drug.
- d. No study-related assessments are to be carried out before signing of the informed consent form.
- e. Includes height, weight, and waist circumference (height at screening only).
- f. Includes HBsAg, and anti-HCV and HIV antibodies.
- g. For practical reasons, the timing of DEXA may vary from the actual time of the visit, depending on DEXA availability (DEXA appointment). The Visit 2 DEXA can be performed prior to Visit 2 during the screening period, as well as at Visit 2 but must be performed before randomization. The Visit 5 DEXA can be performed ± 4 days from the actual time of Visit 5. It is however to be performed before the last dose of the study drug; in case the DEXA appointment related to Visit 5 is scheduled later in time than Visit 5, study drug intake must be continued until DEXA has been performed.
- h. Predose at Visits 2, 3, and 4; predose and 3 hours postdose at Visit 5.

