- i. Includes LH, FSH, E2, SHBG, leptin, insulin, C-peptide, and HbA1c (HbA1c at Visits 2 and 5 only). Additional back-up samples will be collected at every visit and stored for future, exploratory use.
- j. Recorded in the ePRO diary on an ad hoc basis, but at a minimum twice-daily (morning/evening) from screening to follow-up. Night sweats should be recorded no later than morning upon awakening to start a new day.
- k. Completed in the ePRO diary at the clinical site at any time during the visit.
- l. Paper-based, administered at the clinical site at any time during the visit.
- m. Includes biochemistry, coagulation, and hematology panel (coagulation panel only at screening). Blood samples for clinical laboratory tests should be taken in a fasted state (overnight fast for at least 10 h) for unbiased glucose, insulin, and C-peptide determination.
- n. Includes BALP and CTX.
- o. Includes body temperature (oral), sitting blood pressure and pulse rate (supine after 5 minutes of rest).
- p. Supine 12-lead after 5 minutes of rest.
- q. Study drugs will be dispensed to the subjects at Visits 2, 3, and 4 (one bottle containing 68 capsules at every visit).
- r. The first intake of study drugs (Day 1; Visit 2) will be done at the clinical site (between 7:00 and 10:00 AM), under the supervision of the clinical staff. Study drug intake will be done with a glass of tap water at room temperature. Also on other days of visits, the morning dose of study drug will be taken at the clinical site, under the supervision of the clinical staff, after collection of predose blood samples. Subjects will be instructed not to consume food/fluids for at least 10 hours before their visit to the clinical site (except water intake until 1 hour before). On all other days throughout the treatment period, subjects will be asked to take their morning dose of study drug at home, around the same time of day (preferably between 7:00 and 10:00 AM). Morning intake at home may be done together with a light meal. All evening doses of study drug will be taken at home (preferably between 7:00 and 10:00 PM). Subjects need to record all home study drug intakes in the ePRO diary.

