7. ASSESSMENTS

7.1 TIMING OF ASSESSMENTS

All visits need to be planned in the morning, fasted (for unbiased glucose, insulin, and C-peptide determination). Visit 2 should be planned to allow for first intake of study drugs at the clinical site between 7:00 and 10:00 AM. For each subject, all visits during the treatment period subsequent to Visit 2 should be planned at the same time of the day, in the morning, fasted. A deviation of \pm 1 day is allowed on the visits during the treatment period (Visits 3-5).

At Visits 2 and 5, DEXA will be performed. For practical reasons, the timing of DEXA may vary from the actual time of the visit, depending on the DEXA availability (DEXA appointment):

- The Visit 2 DEXA can be performed prior to Visit 2 during the screening period, as well as at Visit 2 but must be performed before randomization;
- The Visit 5 DEXA can be performed \pm 4 days from the actual time of Visit 5. It is however to be performed before the last dose of the study drug; in case the DEXA appointment related to Visit 5 is scheduled later in time than Visit 5, study drug intake must be continued until DEXA has been performed (study drug intake at home and recorded in the ePRO diary).

An overview of the timing of study drug intake and assessments is given in the [Time and Events Schedule](#).

All assessments will be done predose, except for 3 hours postdose blood sampling for PK and PD assessments at Visit 5 and administration of questionnaires, which can be done at any time during the visit.

7.1.1 *Screening Period (Visit 1)*

Subjects will be given a full explanation of the nature of the study and written informed consent (approved by the local ethics committee) will be obtained according to local requirements before any study-related assessment will be carried out.

Screening (Visit 1) will be performed within 4 weeks prior to the first intake of study drug (with a minimum of 7 days to allow for baseline data collection of Hot Flash Score and Hot Flash Frequency). The visit will consist of screening assessments for eligibility purposes (physical examination, thorough medical history, demographic data, vital signs, ECG, blood/urine samples for PD measurements, clinical laboratory tests, serology, urine drug screen, and urine pregnancy test). In addition, subjects will be trained in the use of the ePRO diary to record their hot flashes severity and frequency, to administer HFRDIS, and to register their study drug intake.

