Collection of hot flashes severity and frequency will be started on an ad hoc basis, but at a minimum twice-daily (morning and evening), via ePRO diary. Data on hot flash severity and frequency collected during the screening period will serve as baseline for Hot Flash Score and Hot Flash Frequency.

An overview of the assessments to be performed at the screening visit is provided in the [Time and Events Schedule](#).

Adverse events and concomitant therapies will be collected from signing of informed consent onwards (screening) through the follow-up visit.

All results from the screening procedure that are needed to evaluate eligibility, including the clinical laboratory results, must be available prior to randomization (Visit 2). Any abnormal assessment at the screening visit will be assessed according to its clinical relevance, and if found relevant, the subject will not be included in the study.

Unscheduled visits may be planned to assess, confirm, and follow-up on an out-of-range clinical laboratory test, vital sign, or ECG value that will determine a subject's eligibility, or in case of a positive urine drug screen. Results of this retest must be available prior to randomization. The result of the retest will be considered for subject eligibility. Findings made during unscheduled visits should be reported in the source documents and in the designated sections of the eCRF.

For screening failures, demographic data, the date of screening and signature of the ICF, and the reason(s) for screening failure will be recorded on the eCRF.

7.1.2 *Treatment Period (Visits 2-5; Weeks 1-12)*

Visit 2 should be scheduled in the morning between 7:00 and 10:00 AM, fasted. In- and exclusion criteria will be reassessed. Eligible subjects will be randomized in a 1:1 ratio to one of the 2 treatment arms (ESN364 90 mg b.i.d. or placebo). Predose assessments for efficacy (questionnaires), PK (ESN364 plasma concentrations), PD (hormone concentrations), and safety (clinical laboratory testing, bone density marker concentrations, vital signs, ECG, and physical examination) parameters will be made to serve as baseline (except for Hot Flash Score and Hot Flash Frequency, for which baseline will be data collected during the screening period).

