Blood samples for clinical laboratory tests will be taken at every visit and should be taken in a fasted state (overnight fast for at least 10 hours) for unbiased glucose, insulin, and C-peptide determination. Physical examination and vital sign assessments will also be made at every visit. An ECG will be recorded at every visit except Visit 4. Levels of the bone density markers BALP and CTX will be assessed at Visits 2 and 5 only.

DEXA will be repeated at Visit 5, before the last dose of the study drug. For practical reasons, the timing of DEXA may vary from the actual time of the visit, depending on the DEXA availability (DEXA appointment). The Visit 5 DEXA can be performed ± 4 days from the actual time of Visit 5. It is however to be performed before the last dose of the study drug; in case the DEXA appointment related to Visit 5 is scheduled later in time than Visit 5, study drug intake must be continued until DEXA has been performed (study drug intake at home and recorded in the ePRO diary).

Adverse events and concomitant therapies will be collected from signing of informed consent onwards (screening) through the follow-up visit.

Compliance towards study drug intake and ePRO completion will be checked at every visit during the treatment period. Compliance towards study drug intake will be assessed by counting returned dosage units in addition to ePRO entries. Any discrepancies between returned dosage units and dosing in the ePRO diary will be discussed with the subject for whom a discrepancy was seen.

An overview of the assessments to be performed during the treatment period is also provided in the [Time and Events Schedule](#).

7.1.3 *Follow-up Period (Visit 6)*

Two to 3 weeks after the last intake of the study drug, subjects will be asked to come to the clinical site for a follow-up visit.

An overview of the assessments to be performed at the follow-up visit is provided in the [Time and Events Schedule](#).

7.1.4 *Unscheduled Visits*

Unscheduled visits can be planned for instance:

- to obtain additional information to ensure safety to the subject. Additional blood and urine samples may be taken at the discretion of the Investigator.

- to collect an additional blood sample for PK assessment if a subject discontinues the study drug due to an AE;

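### Section 7.5.1.3 puts the only post-baseline bone marker sample (BALP, CTX) at Visit 6, off drug; Section 7.1.2 and the Time and Events Schedule put it at Visit 5, on drug

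*Protocol*

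**What the plan says.** Three places in the Protocol set the timing of BALP and CTX.

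- Section 7.5.1.3 (Bone Density Markers), which defines the variable: "Plasma concentrations of the bone density markers BALP and CTX will be assessed at Visits 2 and 6".
- Section 7.1.2 (Treatment Period): "Levels of the bone density markers BALP and CTX will be assessed at Visits 2 and 5 only".
- The Time and Events Schedule: the row "Bone density markers ⁿ", whose footnote reads "Includes BALP and CTX", is marked at Visits 2 and 5 and is empty at Visit 6.

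Section 7.5.2 lists the endpoint as "Changes from baseline over time in BALP and CTX levels" and names no visit. Section 2.2 includes both markers in the secondary objective on safety and tolerability of 12 weeks of ESN364.

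**The concern.** There is one post-baseline sample per subject, so its visit decides what the endpoint measures: the level at the end of treatment (Visit 5) or the level after drug washout (Visit 6). Only the first answers the stated objective.

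The outlying text is also the section that defines the variable. The neighbouring sections on laboratory tests, vital signs, ECG and physical examination send the reader to the Time and Events Schedule for timing. Section 7.5.1.3 fixes its own visits instead, and the protocol states no rule on which text prevails. A site or laboratory that works from that section would skip the Week 12 sample, and the SAP could not repair the loss. If sites read the protocol differently, the change from baseline would mix on-drug and off-drug values.

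Bone safety matters for this compound. Section 1.1.2 presents preserved bone density as part of its expected advantage over existing GnRH products.

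**Working it through.** **1. Reading the schedule.** Because the table was extracted from a PDF, its columns need a check. The bone marker row has the same pattern of marks as the DEXA row, and Section 7.1 says of DEXA: "At Visits 2 and 5, DEXA will be performed". The physical examination row, marked at all six visits, confirms the column count. The bone marker row therefore reads Visits 2 and 5.

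**2. The three texts side by side.**

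| Source | Baseline | Post-baseline |
|---|---|---|
| Section 7.5.1.3 | Visit 2 | Visit 6 |
| Section 7.1.2 | Visit 2 | Visit 5 |
| Time and Events Schedule | Visit 2 | Visit 5 |

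The sections cannot be read as additive (Visits 2, 5 and 6), because Section 7.1.2 restricts sampling to two visits. The log for Amendment 1 does not mention bone markers, so the conflict lies within the current text.

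**3. Treatment status at each visit.**

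- Visit 2: before the first dose. Section 7.1.2 says that predose assessments for "safety (clinical laboratory testing, bone density marker concentrations, vital signs, ECG, and physical examination) parameters will be made to serve as baseline".
- Visit 5: Week 12, while the subject is still taking study drug.
- Visit 6: "Two to 3 weeks after the last intake of the study drug" (Section 7.1.3), so off drug.

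**4. Scheduled on-treatment samples per completing subject.**

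- Section 7.1.2 and the schedule: 1 (Visit 5).
- Section 7.5.1.3: 0 (Visit 2 is predose, Visit 6 is off drug).

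**5. How far off drug Visit 6 is.** The longest mean half-life in Section 1.3 is 7.06 h (women, 180 mg once daily, Day 1). Number of half-lives = days × 24 / 7.06.

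- 14 days: 14 × 24 / 7.06 = 336 / 7.06 = 47.6.
- 21 days: 21 × 24 / 7.06 = 504 / 7.06 = 71.4.

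Essentially no drug is present at Visit 6. This describes the drug only; the protocol gives no recovery time for BALP or CTX.

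**The case against.** The strongest reply is that this is a one-digit slip in one sentence, outvoted by two concordant texts. The protocol repeatedly directs readers to the Time and Events Schedule, and Section 7.1.3 on the follow-up visit lists no assessments of its own but points to that schedule, where the bone marker cell is empty. Most sites would probably sample at Visit 5. This is fair, and it makes total loss of on-treatment data a worst case rather than the expected outcome. It does not remove the contradiction.

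Second, the half-life count shows that the drug has gone, not that the markers have returned towards baseline. This also stands. That a change on treatment may have reversed by Visit 6 is a possibility the document can neither support nor exclude. The narrower point does not need it: a level taken two to three weeks off drug is not the quantity named in the objective.

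Third, no text formally pairs the markers with DEXA, which is an exploratory body composition endpoint and has its own window of ±4 days around Visit 5. The pairing is an inference. Even so, DEXA must precede the last dose, so markers drawn at Visit 6 would fall on the other side of treatment end from the other bone measurement.

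Fourth, the consequences are limited. Safety data are analysed descriptively, significance testing is exploratory, and no withdrawal criterion or stopping rule uses these markers. Subjects who withdraw early are also asked to complete the relevant assessments on that day (Section 8.2). These points limit the severity, but early withdrawals do not supply the endpoint for subjects who complete treatment.

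**Conclusion.** The contradiction is real, and Section 7.5.1.3 is wrong as written. If it is followed everywhere, none of the up to 80 planned subjects has a scheduled on-treatment BALP or CTX value. Under Section 7.1.2 and the schedule, every subject who attends Visit 5 on treatment does. If sites split, the endpoint is a mixture of the two.

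The size of any bias in the marker change cannot be calculated, because it depends on how many sites follow which text and on how quickly the markers recover; the protocol gives neither. The conclusion rests only on the visit definitions and on there being a single post-baseline sample. It should be corrected because that sample is irreplaceable. It does not touch the primary endpoint.

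**What to change.** Change Section 7.5.1.3 to Visits 2 and 5. This agrees with Section 7.1.2, the Time and Events Schedule and the 12-week objective, and puts the sample at the same visit as the second DEXA. Check that the laboratory manual and the site sampling kits carry the same visits.

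Naming the endpoint in Section 7.5.2 as change from baseline to Week 12 would make the intent explicit. It is optional, since once the visit is corrected only one post-baseline time point remains.

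The cost is one line in the protocol and a check of the laboratory manual, with no extra sample or visit. If recruitment has begun, sites should be told promptly, and any sample already taken at Visit 6 should be identified and kept apart from the Week 12 values.
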